Cover Page – Study Protocol

Title: Vagal Nerve Stimulation for Treatment Resistant Major Depression

NCT04990687

August 30, 2022

Vagal Nerve Stimulation for Treatment Resistant Major Depression

A. Background and Study Aims

The goal of this background statement is to outline unmet needs in treating Major Depressive Disorder (MDD) and how non-invasive vagal nerve stimulation (nVNS) could help address those needs. MDD is a common and deleterious illness. The lifetime prevalence of MDD is about 16%. The World Health Organization (WHO) reports that MDD is one of the most common causes of disability in the world, costing society more per year than illnesses such as cancer, heart disease and diabetes. The majority of patients with MDD are poorly served because the treatment they receive is not effective. Thirty nine percent (39%) of patients who receive up to four sequential antidepressant trials continue to demonstrate clinically significant symptoms of MDD. The rate of suicide in severely ill MDD patients is high. Given this data, there is an unmet need to study new and potential therapies for MDD.

Implantable VNS (iVNS), the electrical stimulation of the nervous system to modulate or modify function, has been FDA approved in the United States since the late 1990s. Implantable VNS therapy has been approved for use in epilepsy and depression. It has also been used off-label to treat Parkinson's Disease, essential tremor, dystonia, OCD, severe hearing loss, high frequency hearing loss, obstructive sleep apnea, chronic pain, malignant pain, spasticity, urinary incontinence, and fecal incontinence. VNS therapy is similar to a pacemaker and consists of a small generator and lead implanted under the skin below the collarbone. An attached electrode passes stimulation to the vagus nerve, which in turn sends electrical pulses to the areas of the brain associated with mood regulation and other relevant brain structures. Regular therapeutic delivery adjusts levels of norepinephrine, gamma-aminobutyric acid, serotonin, and aspartate while also increasing blood flow to the thalamus and cortex.

When treating major depression with implanted VNS, the widely held belief is that chronic stimulation is required for therapeutic effect. In trials of implantable VNS in major depression, more patients respond at 12 months than at 3 months. Once depressed patients respond to VNS, the effects have been demonstrated to continue for up to five years with continued stimulation. This finding suggests that VNS gradually changes brain function through neuroplasticity.

electoCore has developed gammaCoreTM, (non-invasive vagus nerve stimulator, nVNS) which is FDA approved for the acute and preventive treatment of cluster and migraine headache. It is approved for adults with cluster headache and \ for adolescents and adults (>12 years of age) with migraine. The portable hand-held nVNS device is external to the body and delivers similar results as the implantable nVNS device, without the need for surgery. The device is about the size of a smartphone and will be held to the neck during the nVNS therapy. Each discrete nVNS stimulation lasts two minutes. We plan to use the recommended dosing schedule used in preventing migraine, since the device has demonstrated safety at that dose/duration and has known effects on the brain. We propose using gammaCoreTM (nVNS) to treat treatment resistant depression (TRD) for up to 6 months.

With this study, we will address the following scientific aims:

- 1) Demonstrate the antidepressant effects of nVNS in human adults with treatment refractory MDD as measured by standard rating scales.
- Confirm gammaCore's™ safety profile in adult patients with TRD.

B. Approach
B1. Study Design

Participants will be medically stable and historically have failed to respond to one or more adequate trials of commercially available antidepressant drugs during the current depressive episode. Five adults with treatment resistant depression will participate in this pilot study. We plan to instruct the participant to self-administer nVNS based on guidance from the manufacturer. The study will use an open-label design. The initial phase will be 3 months and the participant will be seen for monthly follow-up office visits following the screening and baseline visits. If the participant improves after the 3 month trial, as determined by a 25% improvement on the primary outcome measure, the Montgomery-Asberg Depression Rating Scale (MADRS), the participant will continue using the device and be evaluated monthly thereafter.

Dosing will occur three times a day (morning, mid-day and night), each consisting of 2 consecutive 2-minute stimulations delivered on the same side of the neck.

At screening participants will undergo a Mini International Neuropsychiatric Interview (MINI), a physical examination, and ECG, vital signs, Montgomery-Asberg Depression Rating Scale (MADRS), Hamilton Depression Rating scale (HDRS-17), Columbia-Suicide Severity Rating (C-SSRS), Antidepressant Treatment Response Questionnaire (ATRQ), Short form Health Survey (SF-36), and Clinical Global Impression (CGI-S). Laboratory assessment including CBC with differential, TSH with reflex T4, CMP, UA, and UDS will be done at screening. At screening, we will also administer the following self-reported questionnaires to characterize reward sensitivity and other personality features relevant to anhedonia: Social Anhedonia Scale, the Motivation and Energy Inventory and the Physical Anhedonia Scale. The screening period will last up to one week, at which point subjects will present for a baseline visit during which they will receive their device and training on its use.

Participants will be seen on site monthly during the study. Treatment effects will be measured using standard rating scales including the HDRS-17, MADRS, SF-36, CSSR-S, CGI-I, CGI-S, which will be completed at each visit. The following scales will be completed at every other visit following the screening and baseline visits: Social Anhedonia Scale, the Motivation and Energy Inventory and the Physical Anhedonia Scale. At each study visit safety assessments including vital sign assessment and adverse event assessment will be completed. Subjects will also undergo physical examination and an ECG for safety during screening, after 3 months of treatment and at the end of 6 months of treatment.

To assess potential changes in cognition, three tests of cognition will the administered at baseline, month 3, and month 6. The Digit Symbol Substitution Test will measure psychomotor performance. The Digits Forward and Backward Test measures attention and working memory. The Reys Auditory and Verbal Learning Tasks evaluates verbal learning.

Additional design elements are as follows:

Analysis plan: The data will first be screened for outliers and structural problems using analytical and graphical methods. If there are violations of normality assumptions, we will determine if power transformations can address this. Otherwise, we will analyze the data using non- and semi parametric methods.

The primary analysis approach will be a generalized linear mixed model. This approach allows modeling within subject correlations of the data in a repeated measurement design and provides unbiased parameter estimates. Time will be modelled as a within subject variable. The main variable of interest in the model will be the time*Tx interaction term. To account for baseline differences between participants we will include random effect terms for each subject.

B2. Inclusion/Exclusion Criteria

Participants will be recruited from the outpatient clinic at the University of Alabama at Birmingham Department of Psychiatry and Behavioral Neurobiology. All recruiting efforts will be coordinated through the existing infrastructure of the Depression and Suicide Center.

Inclusion Criteria:

- 1) Age 18-75 years old
- 2) Sufficient fluency in English to understand testing procedures and provide written informed consent
- 3) A Hamilton Depression Rating Scale total score ≥ 18
- 4) A DSM 5 diagnosis of MDD based on the MINI.

Exclusion Criteria:

- 1) Evidence of alcohol or other substance use disorder in the past 3 months
- 2) For females: current pregnancy or lactation (women of reproductive potential must have a negative urine pregnancy test at screening).
- 3) Depressed patients who have failed at least one adequate antidepressant trial during the current depressive episode based on the ATRQ.
- 4) Diagnosis of other primary psychiatric disorder (defined in this case as being the main focus of treatment) as determined by the MINI, such as: bipolar disorder, personality disorders, psychotic disorders, post-traumatic stress disorder, obsessive-compulsive disorder, dissociative disorders, eating disorder, or cognitive task due to neurological conditions
- 5) Systolic blood pressure < 150 and/or diastolic blood pressure < 90 at screening
- 6) Post-partum state (being within 2 months of delivery or miscarriage)
- 7) Imminent suicide or homicide risk as determined by the investigator
- 8) Being treated with one of the following medications: benzodiazepines or other CNS depressants.
- 9) No clinically significant neurological disease based on medical history (e.g., epilepsy) or significant head injury.
- 10) Any of the following disorders are exclusionary: Rheumatoid arthritis; Lupus erythematosus; Autoimmune hepatitis; Autoimmune peripheral neuropathy; Autoimmune pancreatitis; Behcet's disease; Crohn's disease; Autoimmune glomerulonephritis; Grave's disease; Guillain-Barre syndrome; Hashimoto's thyroiditis; Autoimmune polymyositis or polymyalgia; Myasthenia gravis; Narcolepsy; Polyarteritis nodosa; Scleroderma; Sjogren's syndrome; Transverse myelitis; Wegener's granulomatosis; History of seizures (only childhood febrile seizures are allowed)
- 11) The presence of clinically significant laboratory findings in the opinion of the investigator including, but not limited to, clinically significant anemia or transaminase elevation is considered exclusionary.
- 12) If the UDS is positive, the subject would be excluded if, in the opinion of the investigator, the positive UDS meant the subject has an active substance use disorder.
- 13) Patients with prior exposure to VNS therapy whether using an implantable or external device will be excluded.
- 14) An active implantable medical device, such as a pacemaker, hearing aid implant, or any implanted electronic device
- 15) A metallic device, such as a stent, bone plate, or bone screw, implanted at or near the neck
- 16) An open wound, rash, infection, swelling, cut, sore, drug patch, or surgical scar(s) on the neck at the treatment location
- 17) Patients diagnosed with narrowing of the arteries (carotid atherosclerosis)
- 18) Patients who have had surgery to cut the vagus nerve in the neck (cervical vagotomy)
- 19) Patients with clinically significant hypertension, hypotension, bradycardia, or tachycardia

B2. Assessments of clinical symptoms, cognition and functioning

Depressive symptoms will be assessed with the Hamilton Depression Rating Scale 17 item version and the Montgomery Asberg Depression Rating Scale. We will also administer the following self-reported questionnaires to characterize reward sensitivity and other personality features relevant to anhedonia: Social Anhedonia Scale, the Motivation and Energy Inventory and the Physical Anhedonia Scale.

C. References

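### The primary parameter is a time-by-treatment interaction, but all five participants receive the same open-label treatment and Tx is undefined, so it cannot be estimated

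*Protocol*

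**What the plan says.** The analysis plan in protocol section B1 specifies a generalized linear mixed model with time as a within-subject factor. It then names the target: "The main variable of interest in the model will be the time*Tx interaction term". On the random part it adds: "To account for baseline differences between participants we will include random effect terms for each subject". The SAP, dated April 3, 2024, repeats this text unchanged about 19 months after the protocol of August 30, 2022.

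The design paragraphs of section B1 say:

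- **Size:** "Five adults with treatment resistant depression will participate in this pilot study".
- **Masking and arms:** "The study will use an open-label design". Neither document mentions a sham, control arm, randomisation, crossover or dose group.
- **Start of treatment:** "subjects will present for a baseline visit during which they will receive their device and training on its use".
- **Regimen:** one schedule for everyone, beginning "Dosing will occur three times a day".
- **After month 3:** "If the participant improves after the 3 month trial, as determined by a 25% improvement on the primary outcome measure", the MADRS, "the participant will continue using the device and be evaluated monthly thereafter".

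Tx is not defined in either document.

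**The concern.** A time-by-treatment interaction asks whether the course over time differs between treatment conditions, so Tx must take at least two values. The design as described supplies one. The term then carries no information beyond time, and a model fitted as written either fails or silently loses a column.

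The second outcome is the more harmful. The surviving time coefficient could be reported under the interaction's name, as if a treatment contrast had been tested. It would in fact be an uncontrolled pre-post change, which cannot separate a device effect from natural course, regression to the mean or placebo response. This matters because the protocol's first aim is to demonstrate an antidepressant effect.

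Time is already in the planned model, but the plan does not make its effect primary, tie it to a visit, or say whether time is linear or categorical. Those choices would fall to the analyst after the data are in.

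**Working it through.** The documents give no power, SD or sample-size calculation, so there is no stated figure to reproduce. The question is whether the interaction can be estimated.

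**Inputs.** Five participants; visits at baseline and monthly to month 3, or to month 6 for those who continue; screening up to one week before baseline (all protocol section B1). The coding of time is not stated, so both forms were tried. Complete data are assumed.

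**Method.** Build the fixed-effects matrix (intercept, time, Tx, time × Tx) and compare its rank with and without the interaction columns. If the rank does not rise, the interaction adds nothing.

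| Coding of Tx | Visits | Linear time: rank of columns (without interaction) | Categorical time: rank of columns (without interaction) |
|---|---|---|---|
| Always 1 | Months 0–3 | 2 of 4 (2) | 4 of 8 (4) |
| Always 1 | Months 0–6 | 2 of 4 (2) | 7 of 14 (7) |
| 0 at baseline only | Months 0–3 | 3 of 4 (3) | 4 of 8 (4) |
| 0 at baseline only | Months 0–6 | 3 of 4 (3) | 7 of 14 (7) |
| 0 at screening and baseline | Screening to month 3 | 4 of 4 (3) | 5 of 10 (5) |
| 0 at months 4–6 for 1 to 4 non-continuers | Months 0–6 | 4 of 4 (3) | 10 of 14 (8) |

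**Reading the table.**

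1. With Tx = 1 throughout, time × Tx equals time, row for row.
2. With linear time and only baseline off treatment, time × Tx is 0 at month 0 and equals time afterwards. That is again the time column.
3. With screening and baseline both off treatment, linear time reaches full rank. The pre-treatment slope then rests on two readings about a week apart. Placing screening at −0.25 month, with residual SD 1, the variance per participant is 2/0.25² = 32 for the pre-treatment slope and 1/2 for the slope over months 1, 2 and 3. The standard error of their difference is √((32 + 0.5)/5) = √6.5 = 2.55 residual SDs per month. A plain time slope over the same visits has a standard error of 0.16. With categorical time this coding achieves nothing.
4. Coding non-continuers as off device makes some terms estimable. Under the month-3 rule, however, those participants are the ones who missed 25% improvement, so the contrast is selected on the outcome. The documents do not schedule off-device assessments for them.
5. Random effects for each subject leave the fixed-effects columns as they are and supply no treatment contrast.

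**What can be estimated.** A time-only model for months 0–3 has full rank: 2 of 2 (linear) or 4 of 4 (categorical). For the mean change from baseline to month 3, the 95% half-width in SDs of the change is:

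- **Paired t, 4 df:** 2.776/√5 = 1.24.
- **Random intercept, four complete visits, (5 − 1)(4 − 1) = 12 df:** 2.179/√5 = 0.97. This assumes equal variance and equal correlation across visits.

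The documents give no SD of change. For an assumed 6 to 12 MADRS points the half-width is 7.4 to 14.9 points (paired t) or 5.8 to 11.7 points (random intercept). With four completers the multipliers are 3.182/√4 = 1.59 and 2.262/√4 = 1.13.

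**The case against.** The protocol never uses the term single-arm; that is inferred from the absence of any comparator and from everyone receiving the device. Tx could also be meant as a time-varying indicator, and two such codings make at least some terms estimable. Finally, this is a five-person pilot with no stated alpha or hypothesis test, and the defect touches no dosing, safety or continuation decision.

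The inference is fair to point out, and the conclusion is limited to the one-group reading. But nothing in either document supports another reading, and if a comparator was intended, leaving it and Tx undescribed is itself a defect in the primary analysis. Neither time-varying coding is specified. One is formally estimable but nearly uninformative, the other compares groups formed by the outcome, and neither supplies a concurrent control. Small size excuses imprecision; it does not excuse a primary parameter that the design cannot deliver.

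One part of the objection does stand. Month 3 is a choice, since treatment may run to six months and assessments are scheduled then. It is the better-supported choice because continued use and evaluation after month 3 depend on response.

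**Conclusion.** The plan is wrong as written. On the one-group design that section B1 describes, the named primary parameter cannot be estimated with either form of time, and coding baseline alone as off treatment does not rescue it. This rests on the inference that no comparator exists and on Tx being undefined; it does not depend on any assumed SD or effect size.

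The SAP had the opportunity to correct the sentence and did not. Because it concerns the primary parameter, it must be fixed before results are reported. The precision figures are secondary: they show what the replacement analysis can offer, and the MADRS-point ranges depend on an assumed SD.

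**What to change.** In both documents, delete Tx and time × Tx and state:

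> The primary parameter is the mean within-participant change in MADRS from the last pre-treatment score to month 3, with a 95% CI.

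Also:

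- **Pre-treatment score.** Use the baseline visit if MADRS is confirmed as done there. Section B1 lists it explicitly at screening and only implies it at baseline. If screening must serve, note that MADRS was then taken at the same visit as the screening Hamilton score; entry requires a Hamilton score of at least 18, which makes regression to the mean more likely.
- **Timepoint.** Give the reason for month 3: device use and evaluation afterwards depend on 25% MADRS improvement.
- **Method.** Say whether a paired analysis or the mixed model gives the estimate and, for the model, how time is coded. Attach any precision figure to its method (about 1.24 SD or 0.97 SD).
- **Interpretation.** State that the change is uncontrolled and cannot by itself be attributed to nVNS.
- **Disclosure.** If data have been examined, date the change and say so.

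The cost is a few sentences and a more modest claim. Conduct, enrolment and data collection do not change.

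### With no comparator described, the plan's time*Tx term cannot be estimated; its mixed model for five people names no random slope or degrees-of-freedom rule, so a random-intercept reading gives too narrow an interval if rates of change differ

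*Protocol*

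**What the plan says.** The analysis plan in Protocol section B1 and the whole analysis text of the SAP are the same two paragraphs. They name a generalized linear mixed model and give these details:

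- Time: "Time will be modelled as a within subject variable". Whether it enters as a linear trend or as visit categories is not stated.
- Target: "The main variable of interest in the model will be the time*Tx interaction term".
- Random effects: "To account for baseline differences between participants we will include random effect terms for each subject".
- Rationale: "This approach allows modeling within subject correlations of the data in a repeated measurement design and provides unbiased parameter estimates".
- If normality fails and a power transformation does not help: "Otherwise, we will analyze the data using non- and semi parametric methods".

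Section B1 also gives the design: "The study will use an open-label design", and "Five adults with treatment resistant depression will participate in this pilot study". MADRS is the primary outcome measure. It is rated at screening and at the visits, which are monthly after baseline, and the initial phase lasts three months.

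Neither document states a random slope, a covariance structure, an estimation method, a degrees-of-freedom method, a significance level or a confidence level.

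**The concern.** With one treated group, treatment does not vary, so an interaction of time with treatment has nothing to contrast. What remains is the time effect, and its precision depends on details that the plan leaves open.

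The only purpose given for the subject effects is to absorb differences at baseline, which describes a random intercept. Such a model assumes that all participants share one true rate of change. If they do not, the variation between their slopes is treated as visit-to-visit noise and averaged over 14 residual degrees of freedom, when only five independent slopes carry that information. The mean change then looks more precise than it is.

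Mean MADRS change and its interval are the main efficacy result that this pilot can report. Two analysts following the text could report different intervals from the same five people.

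The route from normality check to transformation to an unnamed alternative is a second, separate problem. Five people give a normality check little to work on, yet it may decide the primary method once the outcomes are known.

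**Working it through.** The documents contain no power calculation, variance or significance level, so there is no figure to reproduce. The check shows how large the effect could be.

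**From the protocol:** n = 5 participants; visits at baseline and months 1, 2 and 3, so T = 4.

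**Assumed:** two-sided 5% level; linear time; true mean change of zero; residual SD σ = 4 MADRS points; SD of true slopes between participants τ = 0, 0.5, 1 or 2 points per month.

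**Step 1, closed form for complete data.**

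- Sum of squared centred times: S = 2.25 + 0.25 + 0.25 + 2.25 = 5.
- Residual df of the random-intercept model: n(T − 1) − 1 = 14.
- True variance of the mean slope: (τ² + σ²/S)/n = (τ² + 3.2)/5.
- Variance the random-intercept model reports on average: [σ² + τ²·S·(n − 1)/14]/(nS) = (16 + τ²·20/14)/25.

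| | τ = 0 | τ = 0.5 | τ = 1 | τ = 2 |
|---|---|---|---|---|
| True variance | 0.640 | 0.690 | 0.840 | 1.440 |
| Reported variance | 0.640 | 0.654 | 0.697 | 0.869 |
| Reported SE / true SE | 1.00 | 0.97 | 0.91 | 0.78 |

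**Step 2, rejection rates of a nominal 5% test** (simulation, 200,000 trials per column).

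| | τ = 0 | τ = 0.5 | τ = 1 | τ = 2 |
|---|---|---|---|---|
| Random intercept, t on 14 df | 5.0% | 5.6% | 7.1% | 12.1% |
| Random intercept, Wald z | 7.0% | 7.7% | 9.6% | 15.3% |
| Categorical visits, month-3 contrast, t on 12 df | 5.0% | 5.4% | 6.6% | 10.4% |
| Categorical visits, overall F test | 4.9% | 5.0% | 5.1% | 5.9% |
| Five participant slopes, t on 4 df | 5.0% | 5.1% | 5.0% | 5.0% |
| Random slope with t on 4 df; random intercept with t on 14 df when slope variance is estimated as zero | 3.0% | 3.3% | 3.8% | 4.8% |

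With residual SD varied from 3 to 5, the random-intercept t test rejects 5.4 to 5.9% at τ = 0.5, and 6.3 to 15.6% over τ = 1 to 2.

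**Step 3, mean 95% half-width for the three-month change, in MADRS points.**

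| | τ = 0 | τ = 0.5 | τ = 1 | τ = 2 |
|---|---|---|---|---|
| Random intercept, t on 14 df | 5.1 | 5.1 | 5.3 | 5.9 |
| Five slopes, t on 4 df | 6.3 | 6.5 | 7.2 | 9.4 |
| Random slope with the zero-variance rule above | 6.4 | 6.6 | 7.2 | 9.4 |

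At τ = 0 the five-slope interval is 6.26/5.06 = 1.24 times as wide.

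**Step 4, rank-based fallback.** The smallest two-sided p-value of an exact signed-rank or sign test with five participants is 2/2⁵ = 0.0625, so neither can reach 5%.

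**The case against.** The strongest reply is that the harm depends on choices the plan does not make. The plural wording on random effects, and the sentence on within-subject correlation, leave room for slopes. If true slopes are equal, the random-intercept t interval is correct. At a slope SD of 0.5 the inflation is slight. Time could equally be a visit factor, and then the overall F test is almost unaffected. The plan also never names a mean slope or an interval as its result. All of this stands, and it limits the finding to a conditional one. It does not remove the gap: the text also permits a Wald z interval, which is too narrow for five people even with equal slopes, and the named interaction has to be replaced in any case.

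Two stronger readings are tempting and are not supported.

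- A reader might infer that a random-slope mixed model is unsuitable as the primary analysis, because with five people the slope variance is often estimated as zero (55, 51, 43 and 23% of trials across the four columns). Within those trials a random-intercept interval can be too narrow. Over all trials, however, the procedure rejects only 3.0 to 4.8%, with half-widths close to those of the five-slope method. Choosing between the two is a matter of preference.
- A reader might infer that months 4 to 6 may be reported only descriptively, because continuation depends on the month-3 response ("If the participant improves after the 3 month trial, as determined by a 25% improvement on the primary outcome measure"). That dependence is on an observed score, which a correctly specified likelihood model can accommodate.

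**Conclusion.** The point holds in conditional form. The plan's main term cannot be estimated in the design described, and the model that remains is under-specified for five people. On its most natural reading, the interval for linear change or for the month-3 contrast is too narrow if participants' true rates of change differ. With t-based inference the illustrative size runs from negligible (5.6% at a slope SD of 0.5) to material (12.1% at a slope SD of 2). These figures rest on an assumed residual SD of 4, complete data to month 3 and linear slopes. A reader might infer that the reported interval will in fact be too narrow. The documents do not support that, because they give no variances and do not say whether slopes differ.

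The normality-driven choice of method is a defect in its own right and needs no variance assumption.

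**What to change.** In both the protocol and the SAP:

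1. Replace the time-by-treatment target with the change in MADRS from baseline to month 3. Say whether time is linear or categorical, and which pre-treatment rating is the baseline value.
2. Name one primary analysis in advance that lets participants' changes differ and uses small-sample degrees of freedom. Either of these will do:
   - the existing mixed model with a random slope and Kenward-Roger or Satterthwaite degrees of freedom, with per-participant slopes or month-3 changes and t on (participants analysed − 1) df as the named fallback if the model does not fit; or
   - that per-participant analysis as primary.
3. Do not let a normality check select the primary method. Keep transformations and rank tests as named sensitivity analyses, and note the 0.0625 floor of the exact signed-rank and sign tests at n = 5.
4. Show all individual trajectories.

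The change is to wording only and needs no new data. Its cost is precision. If slopes are in fact equal, the per-participant interval is about 24% wider than needed. If only four participants are analysed, the t multiplier rises from 2.78 (4 df) to 3.18 (3 df), and at a slope SD of 1 the mean half-width rises from 7.2 to 9.0 points.

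### Exclusion criterion 3 bars the treatment-resistant patients the study exists to enrol, and no inclusion criterion requires resistance

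*Protocol*

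**What the plan says.** The Protocol names its population consistently until it reaches the eligibility list. The title refers to treatment-resistant major depression. The first aim in section A is to "Demonstrate the antidepressant effects of nVNS in human adults with treatment refractory MDD as measured by standard rating scales", and the second is to confirm the device's "safety profile in adult patients with TRD". Section B1 (Study Design) says participants will "historically have failed to respond to one or more adequate trials of commercially available antidepressant drugs during the current depressive episode", and then: "Five adults with treatment resistant depression will participate in this pilot study".

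Section B2 (Inclusion/Exclusion Criteria) has four inclusion items: an age range, fluency in English, a minimum Hamilton score of 18, and "A DSM 5 diagnosis of MDD based on the MINI". None concerns treatment history.

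Under the heading "Exclusion Criteria", item 3 is: "Depressed patients who have failed at least one adequate antidepressant trial during the current depressive episode based on the ATRQ".

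The SAP repeats the Protocol's analysis paragraphs and says nothing about eligibility.

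**The concern.** The numbered list is the rule against which eligibility and protocol deviations are judged. As written, it turns away the patients described in B1 and admits patients who have failed no adequate antidepressant in the current episode. There are two ways to run the trial under this text, and neither is sound:

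- **The list is followed literally.** The sample then has no treatment-resistant patients by the Protocol's own definition, and neither aim can be addressed.
- **Item 3 is informally read in reverse.** The intended patients are then enrolled, but each of them meets a written exclusion criterion.

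With five participants, either course can affect the whole sample. A reader of the results could not tell from the Protocol which kind of patient was studied.

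**Working it through.** The documents give no figure to reproduce. The check is a logical comparison of the eligibility statements.

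**Inputs**

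| Source | Condition on treatment history |
|---|---|
| Protocol B1, population | One or more adequate trials failed, current episode: required |
| Protocol B2, exclusion 3 | One or more adequate trials failed, current episode, by ATRQ: excluded |
| Protocol B2, inclusion 1 to 4 | None |
| Protocol section A, both aims | Treatment-refractory or treatment-resistant depression |
| SAP | None |

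**Step 1. Both passages on one scale.** Let F be the number of adequate antidepressant trials failed in the current episode.

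- B1 requires F ≥ 1.
- Exclusion 3 removes everyone with F ≥ 1, which leaves F = 0.
- F ≥ 1 and F = 0 cannot both hold, so the overlap is empty.

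**Step 2. Does other text reopen the overlap?** No inclusion item refers to F, no exception to exclusion 3 is stated, and the SAP is silent.

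**Step 3. Effect on the planned sample.** Suppose k of the 5 participants have F ≥ 1, so that 5 − k have F = 0. The k participants meet exclusion 3, and the 5 − k fall outside B1. The number in conflict with one section or the other is k + (5 − k) = 5 for every k from 0 to 5. Under the literal list k = 0, so 0 of 5 belong to the intended population.

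**Step 4. Sensitivity to the instrument.** Exclusion 3 counts failures by the ATRQ; B1 names no instrument. Write F_B1 for the count behind B1 and F_ATRQ for the count behind exclusion 3. The overlap is strictly empty if every patient with F_B1 ≥ 1 also has F_ATRQ ≥ 1. Otherwise the only patients who satisfy both sections are those with a failure by history that the ATRQ does not count as adequate. The ATRQ is the only treatment-history instrument among the screening assessments in B1, so this reading would limit enrolment to patients whose resistance that instrument does not confirm.

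**Step 5. Would deleting exclusion 3 be enough?** No. With the item gone, the list places no condition on F, so patients with F = 0 and F ≥ 1 would both pass. The list enforces B1 only if the requirement is stated as an inclusion criterion.

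**The case against.** The strongest reply is that this is an evident drafting slip with recoverable intent. The title, both aims and B1 agree, and only exclusion 3 points the other way. The same list has two other items phrased like conditions for entry: exclusion 5, on blood pressure below stated limits, and exclusion 9, which begins with a negation and concerns neurological disease. An inclusion item in the wrong list fits that pattern. On this view site staff would have understood what was meant, and enrolment of the wrong patients is possible but not shown.

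Much of this stands. The documents do not say which rule was applied, that staff screened literally from the list, or whether anyone has been enrolled. The empty overlap also depends on the two sections counting failures in the same way, which is likely but unstated. Nor do the documents compare improvement by number of failed trials, so no direction or size of bias in the MADRS change can be claimed.

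The contradiction itself is not answered. A plausible cause does not change what the criterion says. With several items apparently reversed, a reader cannot safely decide which exclusions to apply as written and which to invert.

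**Conclusion.** The concern holds. Exclusion 3 and B1 apply opposite rules to the same group of patients, and nothing else in the Protocol or SAP reconciles them. Read literally, the eligibility list admits 0% of the population named in the title, B1 and both aims.

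This rests on one assumption: that B1's failures would also be counted by the ATRQ. Without it, a narrow overlap remains in principle (step 4), but it does not make the text workable.

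This is an internal inconsistency, most likely a misplaced item rather than a deliberate choice. It must be fixed because, followed as written, the criterion enrols patients about whom the study asks no question. How many actual participants are affected cannot be determined from the documents.

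**What to change.** - **Amend section B2.** Move the sentence now at exclusion 3 to the inclusion list as criterion 5, keeping its threshold, its time frame and the ATRQ as the instrument. Delete exclusion 3 and renumber.
- **Align B1.** State there that failure is judged by the ATRQ, so that both sections count it in the same way.
- **Review the rest of the list in the same amendment.** Exclusions 5 and 9 also read like entry conditions. The sponsor should establish what each was meant to say and reconcile the wording.
- **Account for anyone already enrolled.** The Protocol is dated August 30, 2022 and the SAP April 3, 2024, and neither gives enrolment status. If participants have been enrolled, record each person's ATRQ result and the version of the rule applied, and report both with the results. A prospective amendment alone would not settle their eligibility.

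The change to item 3 takes one line and adds no visit, assessment or participant, because the ATRQ is already administered at screening. The remaining cost is the review of the other items and the record check for anyone enrolled.
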